7.4.1.6 Monitoring of Subjects With Adverse Events

Adverse events are recorded and assessed continuously throughout the trial (see Section 7.4.1.3) and are assessed for final outcome at the 28-Day Safety Follow-up visit. After the 28-Day Safety Follow-up visit, only AEs that are deemed attributable to the trial drug by the Investigator should be documented until the 10-Week Safety Follow-up visit, defined as 10 weeks (± 2 weeks) after the last trial drug administration.

All SAEs ongoing at the 28-Day Safety Follow-up visit must be monitored and followed up by the Investigator until stabilization or until the outcome is known, unless the subject is documented as "lost to follow-up". In addition, all trial drug-related SAEs occurring after the 28-Day Safety Follow-up visit and ongoing at the Safety Follow-up visit must be followed up in the same manner. Reasonable attempts to obtain this information must be made and documented. It is also the responsibility of the Investigator to ensure that any necessary additional therapeutic measures and follow-up procedures are performed.

7.4.2 Pregnancy and In Utero Drug Exposure

Only pregnancies considered by the Investigator to be related to trial treatment (for example, resulting from a drug interaction with a contraceptive medication) are considered to be AEs; however, all pregnancies with an estimated conception date during the period defined in Section 7.4.1.3 must be recorded by convention in the AE page / section of the eCRF. The same rule applies to pregnancies in female subjects and to pregnancies in female partners of male subjects. The Investigator must also notify the Sponsor or designee in an expedited manner of any pregnancy using the Paper Pregnancy Report Form, which must be transmitted according to the same timelines as described for SAE reporting in Section 7.4.1.4.

Investigators must actively follow up, document and report on the outcome of all these pregnancies, even if the subjects are withdrawn from the trial.

The Investigator must notify the Sponsor or designee of these outcomes using the Pregnancy Report Form. If an abnormal outcome occurs, the SAE Report Form will be used if the subject sustains an event and the Parent-Child / Fetus Adverse Event Report Form if the child / fetus sustains an event.

Any abnormal outcome must be reported in an expedited manner as described in Section 7.4.1.4, while normal outcomes must be reported within 45 days after delivery.

In the event of a pregnancy in a subject occurring during the course of the trial, the subject must be discontinued from trial medication immediately. The Sponsor or designee must be notified without delay and the subject must be followed as mentioned above.

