3.5.7 Embryofetal Toxicity

Embryofetal toxicities are a known risk of the PD-1 / PD-L1 targeting class. Animal models link the PD-1 / PD-L1 signaling pathway with maintenance of pregnancy through induction of maternal immune tolerance to fetal tissue. Based on its mechanism of action (MoA), MSB0011359C may cause fetal harm when administered to a pregnant female. An appropriate contraception warning is provided in this clinical protocol. Subjects with pregnancy or in lactation period are prohibited from being enrolled in clinical trials.

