5.3.1.1 Inclusion Criteria for Dose Escalation

1. Ability to understand the purpose of the study, provide signed and dated informed consent, and able to comply with all procedures
2. Male or female subjects aged \geq 18 years
3. Histologically or cytologically proven metastatic or locally advanced solid tumors, for which no effective standard therapy exists or standard therapy has failed
4. Life expectancy \geq 12 weeks as judged by the Investigator
5. ECOG performance status of 0 to 1 at trial entry
6. Must have evaluable or measurable disease at baseline

7. Adequate hematological function defined by white blood cell (WBC) count $\geq 3 \times 10^9/L$ with absolute neutrophil count (ANC) $\geq 1.5 \times 10^9/L$, lymphocyte count $\geq 0.5 \times 10^9/L$, platelet count $\geq 120 \times 10^9/L$, and Hgb ≥ 9 g/dL
8. Adequate hepatic function defined by a total bilirubin level $\leq 1.5 \times ULN$, an AST level $\leq 2.5 \times ULN$, and an ALT level $\leq 2.5 \times ULN$. For subjects with liver involvement in their tumor, AST $\leq 5.0 \times ULN$, ALT $\leq 5.0 \times ULN$, and bilirubin $\leq 3.0 \times ULN$ is acceptable
9. Adequate renal function defined by an estimated creatinine clearance > 50 mL/min according to the Cockcroft-Gault formula or by measure of creatinine clearance from 24-hour urine collection
10. **Highly effective contraception** (that is, methods with a failure rate of less than 1% per year) for both male and female subjects if the risk of conception exists (Note: The effects of the trial treatment on the developing human fetus are unknown; thus, women of childbearing potential and men must agree to use highly effective contraception, defined in [Appendix 2](#) or as stipulated in national or local guidelines). **Highly effective contraception must be used 30 days prior to first trial treatment administration, for the duration of trial treatment, and at least for 4 months after stopping trial treatment.** Should a woman become pregnant or suspect she is pregnant while she or her partner is participating in this trial, the treating physician should be informed immediately.

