7.4.1.3 Definition of the Adverse Event Reporting Period

The AE reporting period for safety surveillance begins when the subject is included into the trial (date and time of first signature of informed consent) and continues through the trial's 28-Day Safety Follow-up visit, defined as 28 days (± 5 days) after last trial drug administration. After the 28-Day Safety Follow-up visit only AEs that are deemed attributable to trial drug by the Investigator should be documented until the 10-Week Safety Follow-up visit, defined as 10 weeks (± 2 weeks) after the last trial drug administration.

Any SAE assessed as related to MSB0011359C must be reported whenever it occurs, irrespective of the time elapsed since the last administration of MSB0011359C.

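### The window for recording pregnancies closes before the required contraception period ends, and the duty to notify and follow later conceptions is unclear

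*Protocol*

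**What the plan says.** **Recording.** Protocol 7.4.2 treats a pregnancy as an AE only if the investigator considers it related to treatment. It then adds that "all pregnancies with an estimated conception date during the period defined in Section 7.4.1.3 must be recorded by convention" in the AE section of the eCRF, and applies the same rule to partners of male subjects.

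**The period referred to.** Section 7.4.1.3 starts it at informed consent and runs it through the "28-Day Safety Follow-up visit, defined as 28 days (± 5 days) after last trial drug administration". From then until the "10-Week Safety Follow-up visit, defined as 10 weeks (± 2 weeks) after the last trial drug administration", only AEs that the investigator attributes to the drug are documented. One exception has no time limit: "Any SAE assessed as related to MSB0011359C must be reported whenever it occurs".

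**Contraception.** Criterion 10 of 5.3.1.1 requires highly effective contraception "for the duration of trial treatment, and at least for 4 months after stopping trial treatment", for women and men. Criterion 11 of 5.3.1.2 says the same for the expansion cohorts. The reason given is that effects on the human fetus are not known.

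**Notification and follow-up.** Section 7.4.2 continues: "The Investigator must also notify the Sponsor or designee in an expedited manner of any pregnancy using the Paper Pregnancy Report Form". That sentence names no conception window. The next one requires active follow-up and outcome reporting, and refers back to the pregnancies just mentioned. The closing paragraph covers a pregnancy in a subject during the trial: medication stops, the sponsor is told without delay, and the subject is followed.

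**The concern.** The protocol sets a precaution period after the last dose and then uses a shorter period, built for adverse events, to decide which pregnancies must be recorded. A subject or partner who conceives late in the precaution period is someone the protocol wanted to protect from conceiving, yet no eCRF entry is required.

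Section 3.5.7 states that "MSB0011359C may cause fetal harm when administered to a pregnant female", and Section 3.5 lists embryofetal toxicity as a safety topic of interest. Information on human pregnancies after exposure to a new agent comes only from cases that are captured and followed to outcome. If sites read the rules differently, the safety database and the clinical database will hold different sets of pregnancies, and some outcomes may never be sought.

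**Working it through.** The plan gives no figure to reproduce; the check is date arithmetic plus a comparison of the rules.

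**Inputs**
- Contraception after the last dose: at least 4 months (Protocol 5.3.1.1 and 5.3.1.2).
- Month length: 30.4375 days (SAP 9.5).
- 28-day visit: 28 ± 5 days, so Day 23 to 33 (Protocol 7.4.1.3).
- 10-week visit: 70 ± 14 days, so Day 56 to 84 (Protocol 7.4.1.3).

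**Contraception period:** 4 × 30.4375 = 121.75 days.

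**Uncovered days** = 121.75 − day on which the window closes. **Uncovered share** = uncovered days / 121.75.

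| Window closes at | Day | Uncovered days | Share |
|---|---|---|---|
| 28-day visit, nominal | 28 | 93.75 | 77% |
| 28-day visit, latest | 33 | 88.75 | 73% |
| 28-day visit, earliest | 23 | 98.75 | 81% |
| 10-week visit, nominal | 70 | 51.75 | 43% |
| 10-week visit, latest | 84 | 37.75 | 31% |
| 10-week visit, earliest | 56 | 65.75 | 54% |

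The two readings should be kept apart: about 94 days (89 to 99) or about 52 days (38 to 66). Because contraception is required for at least 4 months, these are minimum gaps. Neither reading closes the gap, even at the latest permitted 10-week visit.

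**Which reading applies.** Section 7.4.1.3 names the 28-day visit as the end of the reporting period, and its extension is confined to drug-attributable AEs. Most pregnancies are not AEs under 7.4.2, which favours the shorter window. On the other side, 7.4.2 records pregnancies by convention whether or not they are AEs, and pregnancy tests are scheduled at the 10-week visit (7.1.4.2, 7.4.4). The text does not settle it.

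**Scope of each duty for a conception after the window closes**
- *eCRF recording:* not required.
- *Expedited notification:* required if the sentence is read alone; arguably limited if its opening (the investigator must also notify) ties it to the windowed rule just before it.
- *Outcome follow-up:* depends on which pregnancies the back-reference picks up.
- *Closing paragraph of 7.4.2:* covers subjects during the trial, not partners.
- *Related SAEs:* reportable at any time, but only once a serious event has occurred and been judged related.

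**Detection.** The last scheduled pregnancy test is at the 10-week visit, which may in some circumstances be a phone call without assessments (7.1.4.2). The request to inform the physician of a pregnancy applies while the subject or partner is participating (5.3.1). Sections 5.5.2 and 5.7 allow subjects to be withdrawn once the 10-week visit is done, so participation can end before the contraception period does.

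**The case against.** A reader might infer that conceptions after the window go unreported. The documents do not support that. The conception window is attached to eCRF recording; the notification sentence has no window of its own, a pregnancy in a subject during the trial must be notified without delay, and quarterly follow-up contacts continue for subjects who remain in the trial (7.1.4.3). What can be said is that recording is not required and that the other duties are ambiguous.

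A reader might also take Day 28 as the operative limit and quote 77% as the gap. That is one of two tenable readings; the other gives 43%.

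Nor do the eligibility criteria define an exposure period. They set a precaution. The sentence in 3.5.7 concerns dosing during pregnancy. Section 3.2.2 predicts a half-life of about 6 days, so the fraction remaining would be about 2^(−28/6) = 4% at Day 28 and 2^(−70/6) = 0.03% at Day 70. Predicted exposure for conceptions in months 3 and 4 is therefore very small. This stands, and it limits how serious the point is. It does not remove the mismatch: the protocol chose 4 months, and its recording rule does not follow that choice.

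Finally, Appendix 2 on contraception and the consent pages were not available for this review and might give further instructions to subjects.

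**Conclusion.** The point holds as an inconsistency between sections. Mandatory eCRF recording stops about 52 days (38 to 66) before the end of the required contraception period if the window closes at the 10-week visit, or about 94 days (89 to 99) before it if the window closes at the 28-day visit. Whether notification and outcome follow-up extend to conceptions in that interval is unclear, most of all for partners of male subjects.

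The sizes rest on 30.4375 days per month, on contraception lasting exactly the 4-month minimum, and on the visit windows in 7.4.1.3. They measure calendar time outside the rule, not an expected number of pregnancies, for which the documents give no basis. This is a matter of safety data capture. It is worth correcting because the correction is simple, but it affects no endpoint, estimate or analysis.

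**What to change.** Reconcile 7.4.2 and 7.4.1.3 with 5.3.1:

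- In 7.4.2, define a pregnancy window separate from the AE window. Keep its start at informed consent; starting at first dose would drop conceptions between consent and first dose that are covered now. Extend only its end, to the end of the contraception period that 5.3.1 requires.
- State that recording, expedited notification and outcome follow-up all use this window, for subjects and for partners of male subjects.
- Add a question about pregnancy to the existing quarterly follow-up contact in 7.1.4.3.
- Because 5.5.2 and 5.7 let subjects leave after the 10-week visit, instruct them at that visit to report a conception occurring later in the contraception period. Long-term follow-up alone would miss them.

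The cost is a few sentences in the protocol, one added question, one instruction at an existing visit and a few more pregnancy forms. The length of contraception and the testing schedule stay as they are.

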7.4.3 Clinical Laboratory Assessments

It is essential that the Sponsor be provided with a list of laboratory normal ranges before shipment of IMP. Any change in laboratory normal ranges during the trial will additionally be forwarded to the CRO and the Sponsor.

Blood samples will be taken from non-fasted subjects. All routine laboratory analyses will be performed at a laboratory facility local to the investigational site and relevant results must be drawn and checked before administration of MSB0011359C. The report of the results must be retained as a part of the subject's medical record or source documents. Blood samples for the tests listed in [Table 11](#) will be taken from non-fasted subjects during the Screening phase, at the 28-Day Safety Follow-up visit, and during the treatment phase as specified in the Schedules of Assessments ([Table 1](#) and [Table 2](#)). Complete blood count and core serum chemistry must be checked within 48 hours prior to each dose administration.

Serum electrophoresis, ACTH (dose-escalation cohorts only), ANA, RF, T4, TSH, and urinalysis will be assessed at the time points defined in the Schedules of Assessments ([Table 1](#) and [Table 2](#)). If confirmation of a subject's postmenopausal status is necessary, a FSH level will also be performed at Screening, see Section [7.1.1](#).

Table 11 Required Laboratory Panel Tests

Full Chemistry	Hematology
Albumin	Absolute lymphocyte count
Alkaline phosphatase*	Absolute neutrophil count
Alanine aminotransferase *	Hematocrit
Amylase	Hemoglobin
Aspartate aminotransferase *	Platelet count
Gamma-glutamyltransferase	RBC count
Blood urea nitrogen / total urea*	White blood cell count and differential count
Calcium*	Red blood cell morphology**
Chloride*	Reticulocytes
Cholesterol	Mean corpuscular hemoglobin
Creatine kinase	Mean corpuscular volume
Creatinine*	Mean corpuscular hemoglobin concentration
C-reactive protein	
Glucose*	Hemostaseology
Lactate dehydrogenase	Activated partial thromboplastin time
Lipase	Prothrombin time / international normalized ratio
Phosphorus / phosphates*	
Magnesium*	Basic Urinalysis (dipstick, including macroscopic appearance, bilirubin, blood, color, glucose, ketones, leukocyte esterase, nitrite, pH, protein, specific gravity, urobilinogen) Full urinalysis (dipstick plus microscopic evaluation) to be performed only at the Screening and 28-Day Safety Follow-up visits and a basic urinalysis prior to each administration of the IMP.
Potassium*	
Sodium*	
Total bilirubin / indirect bilirubin*	
Total protein	
Uric acid	Totality of binding ADAs
Triglycerides	AFP (HCC cohort only)
	ACTH (dose-escalation cohorts only), ANA, RF, TSH, and T4
Hormone Follicle-stimulating hormone (if applicable)	Hepatitis Screening* Hepatitis B surface antigen, hepatitis B core antibody Hepatitis B DNA (quantitative PCR) ^a Hepatitis C Antibody, Hepatitis C RNA (quantitative PCR) ^a Hepatitis D antibody ^b

ACTH=adrenocorticotropic hormone; ADA=antidrug antibody; ANA=antinuclear antibody; HCC = hepatocellular carcinoma; IMP=Investigational Medicinal Product; PCR = polymerase chain reaction; RF=rheumatoid factor; TSH=thyroid-stimulating hormone; T4=free thyroxine.

* Core serum chemistries

** Only in case of anemia onset assessed as related to study treatment

a If hepatitis B surface antigen positive and hepatitis B core antibody positive, then reflex to quantitative HBV DNA (PCR); if hepatitis B core antibody positive alone, then reflex to quantitative hepatitis B DNA (PCR); if hepatitis C antibody positive, then reflex to quantitative hepatitis C RNA (PCR). If subject is positive for hepatitis B or C, then viral load will be followed by quantitative PCR according to Table 3.

b If hepatitis B surface antigen or hepatitis B DNA positivity at Screening then must check for hepatitis D status (hepatitis D antibody).

If a subject has a clinically significant abnormal laboratory test value that is not present at Baseline, the test will be repeated weekly and the subject will be followed until the test value has returned to the normal range or the Investigator has determined that the abnormality is chronic or stable.

7.4.4 Vital Signs, Physical Examinations, and Other Assessments

The ECOG PS will be assessed at Screening and at subsequent visits as indicated in the Schedules of Assessments (Table 1 and Table 2) and documented in the eCRF.

Body weight will be measured at Screening and at subsequent visits as indicated in the Schedules of Assessments (Table 1 and Table 2) and documented in the eCRF. Body height will be measured at Screening only.

A physical examination will be conducted at Screening and at subsequent visits as indicated in the Schedules of Assessments (Table 1 and Table 2) and documented in the eCRF (detailed description in Section 7.1). Any abnormalities arising or worsening after the signing of the ICF should be documented in the eCRF Adverse Event section (see Section 7.4.1). Abnormal findings are to be reassessed at subsequent visits.

An ophthalmology examination including slit lamp evaluation inclusive of the anterior segment and with visual acuity should be conducted at Screening. At subsequent visits, eye signs and symptoms should be checked. If there are any clinically relevant findings then an appropriate ophthalmology examination including slit lamp evaluation inclusive of the anterior segment and with visual acuity should be obtained within 2 days.

Digital 12-lead ECGs will be recorded in triplicate at Screening and at trial visits as indicated in the Schedules of Assessments (Table 1 and Table 2) until Week 13 (Visit 10). Subsequent ECGs will be obtained as single recordings. For immediate safety assessments, 1 ECG will be locally analyzed at each time point (see Section 7.2.6). All ECGs obtained in triplicate will be formally analyzed to evaluate whether MSB0011359C has any effects on cardiac electrophysiology, and in particular repolarization. Although preclinical data shows no cardiovascular signal, weekly ECG assessments with triplicates and digital recording are justified due to the need to characterize exposure / QTc relationships to facilitate future clinical rationale.

All newly diagnosed or worsening conditions, signs and symptoms observed since Screening, whether related to trial treatment or not, are to be reported as AEs.

For female subjects of childbearing potential, serum β -HCG pregnancy test will be carried out during the Screening phase. A urine or serum β -HCG test will be performed according to Table 1 and Table 2 during the treatment phase, at the 28-Day Safety Follow-up visit, and at the Safety Follow-up visit. Results of the most recent pregnancy test should be available prior to the next dosing of IMP. Subjects who are postmenopausal (age-related amenorrhea ≥ 12 consecutive months and if needed FSH > 40 mIU/mL [in the postmenopausal range] as outlined in Section 7.1.1), or who have undergone hysterectomy or bilateral oophorectomy are exempt from pregnancy testing. If necessary to confirm postmenopausal status, an FSH will be drawn at Screening.

7.5 Pharmacokinetics

7.5.1 Dose Escalation Phase

Pharmacokinetic parameters include AUC from the time of dosing to the time of the last observation (AUC_{0-t}), AUC from the time of dosing extrapolated to infinity ($AUC_{0-\infty}$), terminal elimination rate constant (λ_z), C_{max} , time to reach maximum concentration (t_{max}), minimum serum concentration observed postdose (C_{min}), and $t_{1/2}$ (for definitions, see Section 8.5.3.2). Blood samples for the analysis of serum concentrations of MSB0011359C will be drawn in all subjects according to the Schedule of Assessments (Table 1).

CCI [REDACTED]

7.5.2 Expansion Phase

Pharmacokinetic parameters are described in Section 8.5.3.2. Blood samples for the analysis of serum concentrations of MSB0011359C will be drawn in all subjects according to the Schedule of Assessments (Table 3).

7.5.3 Body Fluid

Whole blood (3.5 mL per sample) will be collected for PK assessments. Post-infusion samples should be drawn from a site other than the infusion site (that is, the contralateral arm) on the days of infusion. If the infusion is interrupted, the reason for interruption and the exact infusion times will be documented on the eCRF.

The total amount of blood taken during the first 8 weeks of the trial will not exceed the total of 550 mL and during the first 85 days will not exceed the total of 650 mL.

Further details will be summarized in the Laboratory Manual.

CCI [REDACTED]

[REDACTED]

[REDACTED]

[REDACTED]

CCI [Redacted]

[Redacted]

[Redacted]

[Redacted]

[Redacted]

[Redacted]

CCI [Redacted]

CCI [Redacted]

[Redacted]

CCI [Redacted]

[Redacted]

CCI

[REDACTED]

[REDACTED]

[REDACTED]

CCI

[REDACTED]

CCI

[REDACTED]

CCI

[REDACTED]

[REDACTED]

[REDACTED]

CCI

[REDACTED]

CCI [Redacted]

CCI [Redacted]

[Redacted]

[Redacted]

[Redacted]

[Redacted]

[Redacted]

[Redacted]

[Redacted]

CCI [Redacted]

[Redacted]

[Redacted]

[Redacted]

[Redacted]

[Redacted]

• CCI [Redacted]

CCI [Redacted]

CCI [Redacted]

[Redacted]

[Redacted]

[Redacted]

[Redacted]

[Redacted]

[Redacted]

[Redacted]

7.7 Other Assessments

7.7.1 ADA Analysis

The blood sample for Baseline ADA analysis will be collected before trial treatment start. Further serum samples for ADA analysis will be collected as indicated in the Schedules of Assessments (Table 3).

For subjects who achieve a CR on MSB0011359C therapy and then subsequently develop disease progression after stopping therapy, ADA samples will be drawn prior to the second retreatment infusion, then 2 weeks later, and then every 6 weeks until 6 months after treatment re-initiation.

Samples positive for ADAs will be re-analyzed to determine the titer.

CCI [REDACTED]

